8.3 Description of Study Visits

8.3.1 Screening Visit

Visit 1 (0 – 28 days before therapy): The basic work-up will take place, including medical and sexual history, as well as necessary lab tests (testosterone, prolactin, hematology, chemistry), if not available during the last 12 months prior to screening. Subjects will complete the IIEF questionnaire. We will ensure that patients have 4 attempts for intercourse. Screening visit can occur on same day as first injection + SWT/SHAM. Refer to table 1 for procedures to be performed at the Screening visit.

8.3.2 Treatment Visits: Week 0 – Week 4

Upon evaluation of eligibility, subjects will be randomized to one of the two parallel study groups using an online program, and initiate treatment on the same day.

There will be 5 treatment visits for all groups, each occurring at weekly intervals (± 2 days), for a total duration of five weeks. Subjects will complete a Visual Analogue Scale (VAS) pain score after the end of each treatment. Refer to table 1 for all procedures to be performed at the treatment visits.

8.3.3 Follow Up Visits: Months 3 and 6 Post-Treatment

Follow up visits will occur within 90 ± 14 days (Month 3) and 180 ± 14 days (Month 6) days after final treatment visit. Refer to table 1 for procedures to be performed at the follow up visits visit.

9. Investigational Product

9.1 Preparation of IP

Autologous Platelet-Rich Plasma (PRP) is prepared by taking 120 mL aliquots of anticoagulated blood (120 mL whole blood and 16 mL anticoagulant citrate dextrose formula A) obtained from each treatment subject by venipuncture. Each aliquot is processed by an autologous platelet separator (Arthrex Angel, Arthrex Inc., Naples, Florida) to yield 3-10 mL of PRP from each subject. Platelet poor plasma (PPP) can be

added to PRP to achieve the desired injection volume. This system is FDA approved by 501k for “clinical laboratory or intraoperatively at the point of care for the safe and rapid preparation of platelet poor plasma and platelet concentrate (platelet rich plasma) from a small sample of whole blood or a small mixture of blood and bone marrow”. For patients randomized to the control arm, they will still have their blood drawn, however it will not be processed to make PRP.

[figure not shown]
9.2 Administration of Investigational Therapies

9.2.1 Platelet-Rich Plasma

The patient will be positioned supine. A sterile field will be developed with Betadine prep of the genitalia, sterile gloves and a sterile extremity drape. A total of 20 ml of 1% lidocaine will be drawn up using an 18-gauge needle and will be subcutaneously administered using a 27-gauge needle into the subcutaneous tissue at the base of the penis to obtain a dorsal nerve block. A 1/4-inch Penrose drain will be used as a tourniquet by placing it at the base of the penis and maintaining it in place under tension by a sterile clamp. A maximum of 5mL of PRP will be infused steadily over a two-minute period – approximately 2.5 ml each into the right and left corpus cavernosum. The infusion will be performed at this slow speed (each side over 2 minutes of infusion) to minimize injury to the platelet cells. In the control arm, men will be administered injectable normal saline that will be injected in a similar manner as the PRP.

Following administration of PRP or normal saline, compression of the penis will be achieved with a clenched fist for 20 minutes. At 20 minutes, the tourniquet will be removed, and a compressive dressing will be placed around the penile shaft. The patient will be instructed to remove the compression bandage in 4 hours and to contact the study coordinators if he experiences any problems.

Figure 1: Diagram of PRP Injection

9.2.2 Low Intensity Shockwave Therapy

MoreNova is a Linear Shockwave (LISW) device, which incorporates a shockwave transducer operable to deliver shockwaves to a treatment region confined to a narrow rectangle. Shockwaves generation follows the electromagnetic principle. Linear Shockwaves (LISW), as a treatment for ED has been in evaluation in contemporary medicine. It has been in use for the last five years. The present study will utilize a device called "MoreNova", in which shockwaves are focused onto line segments for improved organ coverage. Shockwaves produced by "MoreNova" are aimed at the left and right corpora cavernosa and the crura. The study is aimed at determining the safety and effectiveness of this new type of LISW in the treatment of ED. The treatment session lasts approximately 20 minutes and may be performed in an office environment. Treatment is applied in the physician's office.

Figure 2: Image of MoreNova SWT Device

In the treatment group, patients randomized will receive 5 weekly sessions, in which 720 shocks of treatment energy will be applied in every session to each treated region (left and right corpora cavernosa and crura). In the sham group, patients will have the same number of sessions, and the machine will be set to deliver 720 shock treatments, but the machine will not fire shockwaves.

9.3 Randomization

On Day 0, participants who remain eligible for the trial will be randomized to one of two groups in a 1:1 ratio. The randomization sequence will be computer generated by the study coordinating team.

9.4 Blinding

The study will remain double-blinded by having both blinded and unblinded study teams. All subjects (active-therapy and placebo groups) will undergo blood collection procedure on day of intervention visits.

Preparation of PRP and normal saline injections will be conducted only by unblinded research team members. In the interest of safety, the study product must be inspected to

ensure it is free of air bubbles, clumping, etc. The 10cc syringes used will be colored and covered in both groups in order to ensure the double-blindness of the study.

For participants allocated to the control arm, a sham procedure will be performed in a manner similar to active shockwave therapy arm. Patients will have the same number of sessions, and the machine will be set to deliver 720 shock treatments, however a shield will be placed over the probes to prevent the shockwaves from being transmitted to the penis. In order to maintain the blind, the technician who administers the study therapies will not be involved in assessing outcomes of the study.

If for important medical reasons unblinding of additional team members is thought to be necessary, the investigator may identify the treatment assignment by obtaining randomization records from unblinded study team.

10. Data Management

Data will be entered from source documents into eCRFs which are maintained in an online research database. The investigator will ensure data integrity by confirming the CRF's are attributable, legible, contemporaneous, original, accurate, and complete.

10.1 Case Report Forms (CRFs)

The Investigator or designee must record all required subject data, and an explanation must be documented for any missing data. This study will use electronic case report forms (eCRF) for data entry and database storage.

10.2 Source Documents

Source data is all information, original records of clinical findings, observations, or other activities in a clinical trial necessary for the reconstruction and evaluation of the trial. Source data are contained in source documents. Examples of these original documents, and data records include: hospital records, clinical and office charts, laboratory notes, memoranda, subjects' diaries or evaluation checklists, recorded data from automated instruments, copies or transcriptions certified after verification as being accurate and complete, and records kept at medical technical departments involved in the clinical trial. All corrections to study data will be made by drawing a single line through the information to be corrected without obscuring it. All corrections will be initialed, dated and explained, if necessary, in accordance with good clinical practice (GCP) guidelines.

10.3 Study Monitoring, Auditing, and Inspecting

The investigator will permit study-related monitoring, audits, and inspections by the IRB, government regulatory bodies, and University compliance and quality assurance groups of all study related documents. The investigator will ensure the capability for inspections of applicable study-related facilities.

11. Data and Specimen Banking

11.1 Storage of Data

Data will be maintained on research team hardware, and subject charts will be stored in a filing room maintained by Department of Urology. Clinical follow up and laboratory data will be stored in a locked room, with access only to authorized personnel. It is up to the

principal investigator's discretion as to how long non-FDA study essential documents are retained.

11.2 Specimen Banking

Bio-specimens will be reserved for future testing and stored at -80 degrees Celsius in equipment maintained by ISCI in the Biomedical Research Building (BRB) (address: [name]). Each specimen must have a corresponding requisition form to track the chain of custody from time of collection to time of processing and/or storage.

12. Safety Monitoring and Reporting

12.1 Adverse Events (AEs)

An adverse event (AE) is defined as any untoward medical occurrence associated with the use of a drug in humans, whether or not considered drug related. An AE can be any unfavorable and unintended sign (including an abnormal laboratory finding), symptom, or disease temporally associated with the study. The event does not need to have a causal relationship with treatment. Common Terminology Criteria for Adverse Events Version 5 (CTCAE) will be used for describing AEs. All urological and/or reproductive system AEs will be recorded. For all other AEs, only events greater than grade 2 will be recorded.

Based on our own pilot data assessing SWT and PRP monotherapy, we have compiled the following data on adverse events (Table 2):

We anticipate there to be few adverse events related to the study. Based on the four published studies and abstracts, including 75 men, only minor adverse events were reported (Bruising 1, Mild Pain 4). No serious adverse events were observed [23-26].

SWT related adverse events	
Transient mild cutaneous purpura	0.10%
Local erythema	0.50%
Local swelling/edema	1.00%
Transient local anesthesia or paranesthesia	1.10%

PPR related adverse events	
Pain greater than 5/10 at time of injection	5.00%
Pain lasting > 5 days	5.00%
Penile bruising	0.00%
Penile fracture	0.00%

12.1.1 Expectedness

An adverse event is considered “unexpected” if it is not listed in the investigator brochure, protocol, ICF, or is not listed at the specificity or severity that has been observed; or, if an investigator brochure is not required or available, is not consistent with the risk information described in the general investigational plan or elsewhere in the current application.

Anticipated adverse events for this study include: Pain, Bruising, Swelling, Edema, Allergy, Penile Fracture, and/or New Penile Curvature.

12.1.2 Severity

Common Terminology Criteria for Adverse Events, Version 5 (CTCAE v5.0) will be used to assess severity of adverse events. All grade 3-5 adverse events, regardless of association with the investigational therapy, will be entered into study database and reviewed at research committee meetings.

12.2 Serious Adverse Events (SAEs)

A serious adverse event (SAE) is defined as an AE which, in the view of the Investigator results in: 1) Death; 2) a life-threatening event (i.e. an event in which the subject was at risk of death at the time of the event; it does not refer to an event which hypothetically might have caused death if it were more severe); 3) inpatient hospitalization of > 24 hours or prolongation of existing hospitalization; 4) a significant disability/incapacity; or 5) a congenital anomaly/birth defect. Other important medical events may be considered SAEs if, in the opinion of the Investigator, they jeopardize the subject or require intervention to prevent one of the other outcomes listed above. Based on prior investigations, we do not anticipate any SAEs related to the study procedures [23-26].

12.3 Treatment Emergent Serious Adverse Events (TE-SAEs)

A treatment emergent serious adverse event (TE-SAE) is defined as any serious adverse event for which there is a reasonable possibility that the investigational product caused the adverse event. For the purposes of safety reporting, “a reasonable possibility” means there is evidence to suggest a causal relationship between the study product/procedures and the adverse event.

13. Data and Safety Monitoring Board (DSMB) Charter

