ROUTE OF ADMINISTRATION	Intracavernosal Injection (PRP) + extracorporeal shockwave therapy (SWT)
SUBJECT POPULATION	60 male subjects between the age of 30-75 with Mild or Mild-to-Moderate ED
STUDY OBJECTIVES	
Primary: To investigate and compare the treatment efficacy of PRP injection + SWT vs placebo injection / SHAM treatment in men with mild-moderate ED, as measured by IIEF.
 
Secondary: To study incidence of adverse events and safety of PRP injection + SWT treatment in men with mild-moderate ED, as measured by IIEF.

INVESTIGATION PLAN	
60 men with Erectile Dysfunction (ED) of organic origin, that meet all of the inclusion and none of the exclusion criteria, will be randomized to receive either PRP+SWT, or placebo/sham in a 1:1 double-blinded fashion.
 
a) Group A (30 subjects): Autologous PRP injection + SWT therapy. All subjects in this group will receive 2 sessions of autologous PRP penile injection with 30 ± 7 day treatment interval. 5mL of PRP will be injected at each session. Additionally, patients will receive a total of 3600 shocks over a five-week period, starting at initial PRP injection.
 
b) Group B (30 subjects): Placebo (Normal Saline) + SHAM. All subjects in this group will receive 2 sessions of normal saline penile injection with 30 ± 7 day treatment interval. 5mL of normal saline will be injected at each session. Additionally, patients will receive SHAM treatment over a five-week period, starting at initial placebo injection.

DURATION OF STUDY	7 months (1 month screening, 5 weeks of therapy sessions, 6 months of follow-up).

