DEFINITION OF ENDPOINTS	
Primary:
 
 - Incidence of treatment emergent serious adverse events (TE-SAEs) in all patients during the study period. 
Secondary:
 
 - Change in IIEF-EF score from baseline to 3 and 6 months post-therapy compared to control group. - Percentage of subjects that achieve minimal clinically important difference (MCID) in IIEF-EF from baseline to 3 and 6 months post-therapy compared to control group, - Percentage of subjects who either decrease or discontinue use of PDE5i after three months post-therapy compared to control group. 
Exploratory:
 
 - Differences in Doppler ultrasound parameters (PSV and EDV) from baseline to 6 months post-therapy compared to control group. - Treatment satisfaction as assessed by EDITS questionnaire in all subjects. -

Protocol Synopsis	
INCLUSION CRITERIA	
 1. Be Male 2. Be 30 to 80 years of age (inclusive). 3. Be able to provide written informed consent. 4. Have a diagnosis of mild to moderate ED (12-21) or mild ED (22-25) based on IIEF-EF questionnaire score. 5. Be in a stable heterosexual relationship, and have a minimum of 2 sexual attempts per month for at least one month prior to enrollment. 6. Agree to comply with all study related tests/procedures.
EXCLUSION CRITERIA	
 1. Previous penile surgery of any kind (except circumcision and condyloma removal), such as penile lengthening, penile cancer surgery, penile plication, grafting. 2. Previous history of priapism, penile fracture, Peyronie's Disease, or penile curvature that negatively influences sexual activity, 3. Abnormal morning serum testosterone level defined as a value lower than 300 ng/dL ($\pm 5\%$). 4. Psychogenic ED as determined by study investigator. 5. Patients using ICI for management of ED 6. Patients with generalized polyneuropathy, neurological conditions, or psychiatric disease (such as bipolar disorder or depression). 7. Have a serious comorbid illness or condition that, in the opinion of the investigator, may compromise the safety or compliance of the subject or preclude successful completion of the study. 8. History of consistent treatment failure with PDE5 inhibitors for therapy of ED. 9. Poorly controlled diabetes as indicated by Hemoglobin a1c > 9%. 10. Use of antiplatelet medication

1. Protocol Title

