2.4 Combination Restorative Therapy for Erectile Dysfunction

The development of ED therapeutics that focus on neurovascular regeneration and repair strategies are of great importance. A large body of *pre-clinical* work has demonstrated the effect of SWT alone (monotherapy) on angiogenesis and progenitor / stem cell recruitment for ED [2, 3, 8-11]. PRP monotherapy importantly is also supported by well-defined mechanistic insights obtained from rigorously conducted animal studies [12-19]. All the previous studies in humans have evaluated either IIEF scores and / or penile Doppler ultrasound hemodynamic parameters, but there has not been evaluation of the treatment as a combination. The proposed mechanisms of both interventions would

suggest that the combination therapy would act in a synergistic manner, with superiority over monotherapy. Success of our proposed work could fundamentally change the standard of care for ED and substantially improve the quality of life for tens of millions of men.

3. Study Objectives

3.1 Primary Objective:

To investigate and compare the safety of PRP and SWT vs placebo/sham treatment in men with mild-moderate ED.

3.2 Secondary Objective:

To study the treatment efficacy of PRP and SWT treatment vs placebo/sham treatment in men with mild-moderate ED.

4. Study Endpoints

4.1 Primary Endpoint (safety):

- Incidence of treatment emergent serious adverse events (TE-SAEs) in all patients during the study period. Adverse events will be recorded at every visit. The following contains a list of the anticipated adverse events:
 - Pain
 - Bruising
 - Swelling
 - Edema
 - Allergy
 - Penile Fracture
 - New Penile Curvature

4.2 Secondary Endpoints (efficacy):

- Change in IIEF-EF score from baseline to 3 and 6 months post-therapy compared to control group.
- Percentage of subjects that achieve minimal clinically important difference (MCID) in IIEF-EF from baseline to 3 and 6 months post-therapy compared to control group,
- Percentage of subjects who either decrease or discontinue use of PDE5i after three months post-therapy compared to control group.

4.3 Exploratory Endpoints:

- Differences in Doppler ultrasound parameters (PSV and EDV) from baseline to 6 months post-therapy compared to control group.
- Treatment satisfaction as assessed by EDITS questionnaire in all subjects.
- Changes in IPSS questionnaire between treatment and control group.
- Perceptions of therapeutic allocation between treatment and control group.

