15.1 Risks to Subjects

We anticipate there to be few adverse events related to the study. Based on the four published studies and abstracts, including 75 men, only minor adverse events were reported (Bruising 1, Mild Pain 4). No serious adverse events were observed [23-26]. After literature review, we believe this product to be of non-significant risk to patients (NSR) and for investigational use in a clinical study protocol.

Based on published studies, we will record anticipated adverse events to patients include: local injection site reaction, penile pain, penile hematoma (bleeding into the tissue), penile swelling, allergic reaction to the anesthetic, local infection, penile fracture, or new penile curvature. In addition, there may be uncommon or previously unknown risks that might occur. We will record every adverse event at every visit systematically.

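### The synopsis makes efficacy the primary objective against its own safety endpoint, and that endpoint (TE-SAE) is filtered by a causality judgement, with no onset window and no stated precision

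*Combined protocol and SAP*

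**What the plan says.** **Objectives and endpoint.** The synopsis gives its primary objective as "To investigate and compare the treatment efficacy of PRP injection + SWT vs placebo injection / SHAM treatment", measured by the IIEF. Its secondary objective is "To study incidence of adverse events and safety of PRP injection + SWT treatment", and it names the IIEF as the measure there too. The synopsis primary endpoint, repeated in Section 4.1, is "Incidence of treatment emergent serious adverse events (TE-SAEs) in all patients during the study period". Section 3.1 gives the primary objective as "To investigate and compare the safety of PRP and SWT vs placebo/sham treatment in men with mild-moderate ED", and Section 3.2 puts efficacy second.

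**Definition.** Under Section 12.3 a TE-SAE "is defined as any serious adverse event for which there is a reasonable possibility that the investigational product caused the adverse event". The next sentence explains a reasonable possibility as evidence suggesting a causal link with the study product or procedures. The section gives no start or end date for onset. It does not say who makes the judgement or whether that person is blinded.

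**Recording.** Section 12.1 records all urological and reproductive events, but limits the rest: "For all other AEs, only events greater than grade 2 will be recorded". Section 15.1 says: "We will record every adverse event at every visit systematically". Section 12.1.2 requires grade 3 to 5 events to be entered whether or not they are linked to the therapy.

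**Analysis.** Section 14.1 names Fisher's exact test for categorical data in general, at alpha 0.05, without mentioning TE-SAEs. Section 14.2 sizes the trial on MCID response, a secondary endpoint. On the expected rate, Section 12.2 says only: "we do not anticipate any SAEs related to the study procedures".

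**The concern.** A reader of the synopsis cannot tell whether efficacy or safety decides the trial. The safety objective there is also tied to an erectile function score, which does not measure adverse events.

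The definition matters more. Treatment emergent ordinarily describes timing: onset after treatment starts. Section 12.3 uses the label for attribution instead. In a sham-controlled trial the comparison between arms is itself the evidence on whether treatment adds serious events. If each event must first be judged possibly related, events are lost before that comparison is made. A blinded judgement costs information from both arms. A judgement made by someone who knows the allocation can also bias the comparison, and Section 9.4 lets the investigator obtain the allocation for important medical reasons, which is a situation an SAE can create.

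Finally, the plan does not say what its primary endpoint can show. With few or no events expected, a reader needs to know which rates a count near zero would leave open.

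**Working it through.** **1. The plan's own figure.** Section 14.2 uses z values 1.96 and 0.84, P = 0.25 and a difference of 0.35:

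2 × (1.96 + 0.84)² × 0.25 × 0.75 / 0.35² = 2.94 / 0.1225 = 24.0 per arm.

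Allowing for 20% attrition, 24 / 0.80 = 30 per arm, 60 in total. The arithmetic reproduces, but it concerns 15% v 50% MCID response. There is no corresponding calculation for TE-SAEs.

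**2. Objectives against endpoints.**

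| Place | Primary objective | Primary endpoint |
|---|---|---|
| Synopsis | Efficacy (IIEF) | TE-SAE incidence |
| Sections 3.1 and 4.1 | Safety, compared between arms | TE-SAE incidence |

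The endpoint agrees in both places. The conflict is between the synopsis objective and the synopsis endpoint, and between the synopsis objective and Section 3.1.

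**3. Recording rule.** Grades above 2 are grades 3 to 5, so under Section 12.1 a non-urological event of grade 1 or 2 goes unrecorded. Allergy is listed as anticipated in Sections 4.1 and 12.1.1, and a mild or moderate case could fall in that gap. To affect the primary endpoint, such an event would also have to be serious, for instance as an important medical event under Section 12.2. That is possible but narrow.

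**4. What Fisher's test would need, if it were used for TE-SAE.** Inputs: two-sided alpha 0.05 (Section 14.1; the 1.96 in Section 14.2 implies two sides) and no events in the control arm (assumed). For k v 0 with n per arm, p = 2 × C(n, k) / C(2n, k).

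- n = 30: 5 v 0 gives p = 0.052; 6 v 0 gives p = 0.024. Six events are needed.
- n = 24: 5 v 0 gives p = 0.0496. Five events are needed.

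Power is then P(X ≥ 6) for X ~ Binomial(30, p), or P(X ≥ 5) for X ~ Binomial(24, p). The active rates below are assumptions, because the documents give none.

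| Assumed active rate (control 0%) | 30 per arm | 24 per arm |
|---|---|---|
| 5% | 0.3% | 0.6% |
| 10% | 7.3% | 8.5% |
| 15% | 29% | 29% |
| 20% | 57% | 54% |

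Power of 80% needs an active rate of about 25% with 30 per arm, or 26% with 24.

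**5. What zero events would show.** The upper end of the exact two-sided 95% interval for 0/n is 1 − 0.025^(1/n).

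- 0/30: 1 − 0.025^(1/30) = 11.6%.
- 0/24: 1 − 0.025^(1/24) = 14.2%.
- 0/60, both arms pooled: 6.0%.
- 0/75, the men in the four cited studies: 4.8%. Only 10 of these had PRP with shockwave (the background table of human studies), and 0/10 gives 1 − 0.025^(1/10) = 30.8%.

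**The case against.** Much can be said for the plan. The primary endpoint is the same in the synopsis and the body, so a reader who infers two rival primary endpoints goes too far: only the objective differs.

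The definition is also milder than it may look. It asks for a reasonable possibility, not proof, and its second sentence reaches procedures, so saline injections and sham sessions can qualify. The trial is double-blind, the DSMB sees adverse events by masked group, and grade 3 to 5 events are entered regardless of association. Most of the all-cause data will therefore exist. This stands, but it bears on what could be tabulated; the primary endpoint as defined still excludes those events.

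Three stronger readings are tempting and unsupported:

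- *The planned test cannot detect a plausible difference.* Fisher's test is not assigned to TE-SAEs, no plausible difference is given, and low power for rare SAEs is inherent in a 60-man Phase I/II pilot.
- *A non-significant result will be read as proof of safety.* No section sets such a rule.
- *The endpoint pools the arms.* The phrase about all patients may only name the population, and Section 3.1 asks for a comparison.

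The conflict between Sections 12.1 and 15.1 is real, but correcting either one would resolve it. The documents give no example of a low-grade non-urological event that would count as serious.

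**Conclusion.** Three wording defects are certain on the face of the protocol: the synopsis objectives contradict its own primary endpoint and Sections 3.1 and 3.2; Section 12.3 defines treatment emergence by attribution, without an onset window; and Section 12.1 conflicts with Section 15.1. The second is the most serious, because it weakens the randomised safety comparison that is the stated primary aim. The third probably changes the SAE count little.

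A fourth defect is an omission: the primary endpoint has no precision statement or estimation plan. The power figures show why a significance test would be a poor substitute. They depend on Fisher's test being the intended method, on no control events, and on active rates that are assumed. The zero-event limits need no assumed rate, only the number of men observed. They do not show the design to be too small for a pilot. They show what the plan should say it can and cannot exclude.

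The choice of a single MCID time point is a separate efficacy question and is not part of this point.

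**What to change.** Before unblinding:

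1. Align the synopsis objectives with Sections 3.1 and 3.2, and delete the clause that makes the IIEF the measure of safety.
2. In Section 12.3, define a TE-SAE as any SAE with onset from the first Day 0 study procedure to the Month 6 visit, regardless of attributed cause. Report related SAEs as a subset, and state who judges relatedness and that they are blinded. Starting at the first procedure matters: the blood draw and the nerve block come before the injection and would be missed by a window that opens at the first injection or shock. Tie the end to the visit itself, because the Schedule of Events places Month 6 at Day 180 while Section 8.3.3 counts 180 days from the final treatment visit. Those two passages need reconciling.
3. Record every SAE whatever its grade or body system, and reconcile Section 12.1 with Section 15.1.
4. In Section 14, report TE-SAEs by arm with exact 95% confidence intervals and an interval for the difference. State that zero events would exclude only rates above about 11.6% with 30 treated men, or 14.2% with 24 (two-sided).

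The cost is protocol wording, slightly more recording, and a plainer safety claim. Sample size and visits are unchanged.
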